Official Title: A Randomized Control Trial to Compare the Effects Between Wearable Robotic System and Robotic Mirror Therapy in Patients With Spastic Hemiplegia Post Botulinum Toxin Injection: Neurophysiological and Behavior Outcomes.

NCT number: NCT04826900

Document Date: 2022/03/18

Background:

Botulinum toxin type A (BoNT-A) injection is an effective treatment for upper-limb spasticity, but lacks in effects on arm-hand capacity. Adding a rehabilitation program after BoNT-A injection was suggested as a way to optimize spasticity treatment outcomes. However, the optimal adjunct treatment, especially for hand function, remains to be established.

Aims:

This randomized single-blind pilot study aimed to investigate and compare the effects between Exoskeletal Robotic Hands therapy (RT) vs Exoskeletal Robotic Hands Training Integrating with Mirror Therapy (RMT) after Botulinum Toxin A Injection for Post-stroke Spastic Fingers.

Participants

Participants with stroke were recruited from a rehabilitation department of a tertiary referral hospital. Patients who had spastic finger flexors, at least 1+ with the Modified Ashworth Scale (MAS) (R. W. Bohannon & M. B. Smith, 1987), interfering with hand function, and needed BoNT- A injections, were screened for eligibility to join the study. The inclusion criteria were: (1) clinical and imagine diagnosis of a first or recurrent unilateral stroke \geq 6 months; (2) the MAS of finger flexors \geq 1+; (3) initial motor part of UE of FMA score ranging from 10 to 55, indicating moderate to severe movement impairment; (4) Mini Mental State Exam score \geq 20; (5) age \geq 18 years ; and (6) could provide written informed consent. The exclusion criteria were (1) bilateral hemispheric or cerebellar lesions; (2) fingers had fixed contracture; (3) severe aphasia or cognition impairment; (4) significant visual field deficits or hemineglect; (5) treatment with BoNT-A \leq 4 months before recruitment or (6) history of orthopedic or other neurologic diseases or medical conditions that would prevent adherence to the rehabilitation protocol.

Methods:

A randomization scheme was used to randomize participants. To minimize possible confounding effects of upper limb motor ability, we stratified participants into groups based on upper limb motor function (FMA UE score: 10-35 or a FMA UE score: 35-55) (Pamela W Duncan, Larry B Goldstein, David Matchar, George W Divine, & John Feussner, 1992) A person who did not involve the other study procedures did the randomization to decide new participants' group allocation when they enrolled, and inform the trainer to conduct their intervention. After BoNT-A injection patients were randomly allocated to 2 groups: RT group, and RMT group,

both groups underwent 24 training sessions (60 minutes /session, 3 sessions/week for 8 consecutive weeks). Assessments were performed before training (T0), after training (T1), and 3 months after training (T2). The primary outcomes were changes in the FMA–Upper Extremity score (FMA–UE, total and distal scores) at T1 from T0. The other measures, including Modified Ashworth Scale (MAS), and Medical Research Council scale (MRC), Action Research Arm test (ARAT), Box and block test (BBT) and Motor Activity Log (MAL) at T1 and all measures at T2 were secondary outcomes.

Data Analysis

The Mann–Whitney U test was used to analyze differences between groups. Wilcoxon’s signed-rank test was performed to assess differences in the parameters between baseline and post-training points. All tests were executed using the SPSS software version 25 (International Business Machines Corp., Armonk, NY) at the $\alpha = 0.05$ level of significance.

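### Does the shared boundary at an FMA-UE score of 35 in the randomisation strata call for a change to the plan?

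*Combined protocol and SAP*

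**What the plan says.** The Participants section admits patients with an "initial motor part of UE of FMA score ranging from 10 to 55". The Methods section then describes the stratification: "we stratified participants into groups based on upper limb motor function (FMA UE score: 10-35 or a FMA UE score: 35-55". The purpose given is "To minimize possible confounding effects of upper limb motor ability".

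On the mechanics, the Methods section says only "A randomization scheme was used to randomize participants", and adds that the allocation was done by a person with no part in the other study procedures, who then told the trainer which intervention to give. It mentions no list structure, block size or rule for a score on the boundary.

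The stratification factor is measured on the same scale as the primary endpoint: "The primary outcomes were changes in the FMA–Upper Extremity score (FMA–UE, total and distal scores) at T1 from T0". For the comparison of arms, the Data Analysis section states "The Mann–Whitney U test was used to analyze differences between groups". Changes within patients are tested with Wilcoxon's signed-rank test. Neither test is described with a stratum term.

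**The concern.** An allocation rule should send each eligible patient to exactly one stratum. Here a patient scoring 35 satisfies both definitions, and no inequality sign or tie rule settles the matter. If each stratum had its own list, and the two lists stood at different points, the choice of stratum for that patient could decide the arm. The gap also falls on the baseline of the primary endpoint, in a study that calls itself a pilot, where one patient may be a noticeable share of a stratum.

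Three things would be at stake: discretion at the moment of allocation, the balance that the stratification is meant to secure, and the ability to rebuild the stratum variable for a later stratified analysis.

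**Working it through.** The document gives no sample size or power figure that bears on this point, so there is no stated figure to reproduce. The check has four parts.

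**1. Size of the overlap.** Inputs: the eligible range 10 to 55 (Participants) and the bands 10–35 and 35–55 (Methods). Whole-number scoring is assumed; the overlap at 35 does not depend on it.

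- Eligible scores: 55 − 10 + 1 = 46.
- Lower band: 35 − 10 + 1 = 26. Upper band: 55 − 35 + 1 = 21.
- Memberships: 26 + 21 = 47 for 46 scores. The bands share 35 only, and no eligible score is left out.
- Share of the range: 1/46 = 2.2%. The other 45 scores are placed uniquely.

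Both natural readings of the slip are complete and free of overlap: 10–34 with 35–55 gives 25 + 21 = 46, and 10–35 with 36–55 gives 26 + 20 = 46.

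**2. How often it could arise.** Two assumptions are needed: scores spread evenly over the 46 values, and a sample size N. The expected number scoring 35 is N/46, and the chance of at least one is 1 − (45/46)^N.

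| N (assumed) | Expected number at 35 | Chance of at least one |
|---|---|---|
| 20 | 0.43 | 36% |
| 30 | 0.65 | 48% |
| 40 | 0.87 | 58% |
| 60 | 1.30 | 73% |

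The chance of two or more is 1 − (45/46)^N − (N/46)(45/46)^(N−1). At N = 30 this is 1 − 0.517 − 0.345 = 0.138, about 14%. At N = 40 it is 1 − 0.415 − 0.369 = 0.216, about 22%. Scores concentrated near the middle of the range would raise all these figures, and scores concentrated elsewhere would lower them.

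**3. What it does to the allocation.** Suppose both strata use the same allocation ratio, so that each assigns RT with probability p. The document does not state the ratio, so this is an assumption. Let q be the chance that a patient scoring 35 is placed in the lower band. If that choice is made without knowledge of the next assignments, the chance of RT is q·p + (1 − q)·p = p, whatever q is. An inconsistent choice between two such patients changes nothing here, since q may differ from patient to patient. Bias needs more: separate lists, knowledge of where each stands, and use of that knowledge. The document describes none of these.

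Balance is barely touched. A score of 35 is one point from 34 and one point from 36, so in either band the patient joins others of nearly the same motor ability.

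**4. What it does to the analysis.** The Mann–Whitney test takes each patient's change score and arm. The signed-rank test takes each patient's paired values. Stratum enters neither, so recoding a patient with a score of 35 from one band to the other leaves every planned statistic as it was.

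**The case for a change.** The strongest argument for a change is that the defect is certain, sits in the allocation rule and would cost almost nothing to remove. The randomisation is described so briefly that nothing else in the document settles where a score of 35 goes. Using an independent person lowers the risk of deliberate steering, but it supplies no rule and does not prove that assignments were concealed. The document does not say who determined the stratum. A reader who wanted to tabulate balance by stratum, or to run a stratum-adjusted sensitivity analysis, could not place such a patient from the text alone.

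Most of this is true as description. The overlap stands, and so does the remark about reconstructing strata. What does not stand is the step from there to harm. If concealment is the worry, its source is the unspecified scheme, which concerns every patient and is a separate matter; tidying the boundary would not cure it. The reconstruction problem affects only an analysis that is not planned, and anyone who ran one could take the stratum from the allocation record. The document is also written in the past tense, so a new boundary would have little prospective effect. All that could be done is to report which band took 35 and whether anyone scored it, which is a matter for the trial report.

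**Conclusion.** The strata share the single score 35, and the document does not say which band takes it. This is an error of notation affecting 1 of 46 eligible whole-number scores, about 2.2% of the range. It does not change the planned tests, hardly affects the balancing aim, and is not shown to bias allocation. Following the plan as written would give equally sound results with either reading of the boundary, so no change is called for.

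The conclusion on the tests needs no assumption beyond the analyses as described. The conclusion on allocation rests on the same ratio being used in both strata and on the stratum being chosen without knowledge of upcoming assignments. The document does not establish the second condition, though its use of a person outside the other procedures points that way. The frequencies given rest on an assumed sample size and evenly spread scores, and serve only to show scale.

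### The scale of the secondary outcomes is not stated: read literally, FMA-UE is a change from T0 at T1 but a raw score at T2, which could cost the T2 comparison much of its power

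*Combined protocol and SAP*

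**What the plan says.** The Methods section gives the primary outcome its scale. It opens with "The primary outcomes were changes in the" FMA-UE score, total and distal, and specifies T1 relative to T0.

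The next sentence covers MAS, MRC, ARAT, BBT and MAL at T1 and every instrument, so also FMA-UE, at T2. It ends "Box and block test (BBT) and Motor Activity Log (MAL) at T1 and all measures at T2 were secondary outcomes". Neither score nor change is attached to any of these.

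The Data Analysis section has two sentences on tests. Between groups, the Mann-Whitney "U test was used to analyze differences between groups", with no variable named and no baseline adjustment. Within groups, the Wilcoxon "signed-rank test was performed to assess differences in the parameters between baseline and post-training points". Both are run "at the $\alpha = 0.05$ level of significance".

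The only baseline range is the inclusion criterion under Participants: "initial motor part of UE of FMA score ranging from 10 to 55". For MAS there is a floor of 1+. For MRC, ARAT, BBT and MAL there is nothing. No sample size, SD, effect size or correlation is given.

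**The concern.** T0 values are collected for every patient, and the within-group tests use them. On the literal wording, the RT versus RMT comparison of secondary outcomes does not. For FMA-UE at T2 that matters, because a raw score in patients who enter anywhere from 10 to 55 largely reflects where each patient started.

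Two things are at stake. First, the T2 comparison of FMA-UE may be much weaker than the T1 comparison of the same instrument. Second, the contrast between visits may mislead: a difference found at T1 and not at T2 would naturally be read as a benefit that faded, when it could arise only because T1 was tested as a change and T2 as a level. Because the wording allows both readings, an analyst could also choose either one after seeing the data and still claim to have followed the plan.

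**Working it through.** The plan has no power figure to reproduce, so everything below the first step rests on assumed inputs, shown over ranges.

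**1. Inputs.** From the documents: FMA-UE at entry 10 to 55, Mann-Whitney test, alpha 0.05. Assumed: two-sided testing, 10 to 30 patients per arm, SD of change 3 to 10 points, change unrelated to the T0 score, FMA-UE scale limits 0 to 66.

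**2. Spread of FMA-UE at T0.** If scores are spread evenly over 10 to 55, variance = 45²/12 = 168.75 and SD = 12.99. Narrower guesses are range/4 = 11.25 and range/6 = 7.5.

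**3. Variance of raw T2 score relative to change** = 1 + (T0 variance)/(SD of change)².

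| SD of change | T0 SD 12.99 | T0 SD 8 |
|---|---|---|
| 3 | 1 + 168.75/9 = 19.75 | 1 + 64/9 = 8.11 |
| 5 | 1 + 168.75/25 = 7.75 | 1 + 64/25 = 3.56 |
| 8 | 1 + 168.75/64 = 3.64 | 1 + 64/64 = 2.00 |

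**4. Power, FMA-UE at T2, true difference of one SD of change, 20 per arm, simple allocation.** Simulated Mann-Whitney tests, T0 uniform on 10 to 55, totals clipped to 0–66. The ranges show variation between simulation runs.

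| SD of change | Change | Raw T2 score |
|---|---|---|
| 3 | 83–86% | 9% |
| 5 | 83–86% | 16–18% |
| 8 | 83–86% | 31–32% |

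Hand check by normal approximation at SD of change 5. Change: standard error 5 × √(2/20) = 1.58, 5/1.58 = 3.16, power Φ(3.16 − 1.96) = 88%. Raw: SD √(25 + 168.75) = 13.92, standard error 4.40, 5/4.40 = 1.14, power Φ(1.14 − 1.96) = 21%. The simulated values are a little lower, as expected for a rank test on a bounded scale.

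**5. The same with the difference fixed at 5 points** (change / raw score, simulated).

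| Per arm | SD of change 4 | 6 | 8 | 10 |
|---|---|---|---|---|
| 10 | 71% / 10% | 38% / 10% | 23% / 9% | 16% / 9% |
| 15 | 89% / 14% | 56% / 14% | 35% / 12% | 23% / 10% |
| 20 | 96% / 19% | 70% / 16% | 46% / 15% | 32% / 14% |
| 30 | 99.7% / 26% | 87% / 24% | 63% / 22% | 45% / 19% |

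The T0-to-T2 correlation implied by these settings runs from 0.96 (SD 4) down to 0.80 (SD 10).

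**6. The other measures.** With equal variances at T0 and follow-up and correlation r, Var(change)/Var(score) = 2(1 − r). Fix the effect so that change has 80% power. Power on the raw score is then Φ(2.80 × √(2(1 − r)) − 1.96), and power adjusted for T0 is Φ(2.80 × √(2/(1 + r)) − 1.96).

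| r | Raw score | Change | T0-adjusted |
|---|---|---|---|
| 0.3 | 91% | 80% | 93% |
| 0.5 | 80% | 80% | 90% |
| 0.7 | 58% | 80% | 86% |
| 0.8 | 42% | 80% | 84% |
| 0.9 | 24% | 80% | 82% |

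In patients, raw scores need 1/(2(1 − r)) times as many: 1.7 times at r = 0.7, 5 times at r = 0.9, the same number at 0.5, and fewer below. The T0-adjusted analysis is at least as good as either at every r shown.

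**The case against.** The strongest reply is that the plan never says raw scores are tested. The sentence on secondary outcomes follows directly on one framed as changes from T0 and may simply continue it. The Data Analysis section also speaks of change from baseline in its within-group test. This stands in part: a reader might infer that the secondary outcomes are defined as raw scores, and the documents do not support so firm a statement. They support only that the scale is unstated and that the literal reading is the raw score.

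A reader might also infer that every secondary comparison is swamped by the 10 to 55 spread. That does not follow. The range belongs to FMA-UE alone. For the other five instruments the loss depends on a correlation that the documents do not give, and below 0.5 the change score is the weaker choice (simulated at r = 0.3, effect 0.8 SD, 20 per arm: change 53%, raw score 67%). Even for FMA-UE, T2 is about five months after T0, so the correlation may be lower than the simulated settings imply.

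A third tempting inference is that stratifying on FMA-UE and then ignoring the strata pushes the true error rate of a raw-score test far below 0.05. It does so only if allocation is forced into balance within strata (simulated error 0.05 to 0.5%). With unblocked randomisation within strata the error rate is nominal (4.4 to 5.6%), and the plan describes no blocking.

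Finally, change scores do not remove a chance T0 imbalance. Under equal variances a T0 difference d leaves about r × d in the raw comparison and −(1 − r) × d in the change comparison. This is correct, and it is why adjustment for T0 is preferable to a plain change score.

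**Conclusion.** The point holds as a gap with a practical consequence, not as a demonstrated error. The plan fixes the scale of the primary outcome and leaves that of every secondary outcome open, with no use of T0 stated in the between-group test.

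For FMA-UE at T2, the literal reading could lose much of the power: about 84% on change against 9 to 31% on raw scores, given 20 per arm, T0 uniform over 10 to 55, SD of change 3 to 8, a true difference of one SD of change and simple allocation. None of these inputs except the 10 to 55 range is in the documents. A less even T0 distribution or a lower correlation would shrink the gap. For MAS, MRC, ARAT, BBT and MAL no size can be given.

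This is a self-described pilot and these are secondary outcomes, so the weight is modest. It is a cheap improvement: the better analysis uses data already collected and also keeps T1 and T2 comparable for FMA-UE.

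**What to change.** Replace the sentence on secondary outcomes with wording to this effect: FMA-UE total and distal at T2 are analysed as change from T0, on the same scale as the primary outcomes; MAS, MRC, ARAT, BBT and MAL at T1 and T2 are compared between groups with the T0 value taken into account.

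In Data Analysis, name the variable for each between-group test. For the other secondary outcomes the preferred method is a T0-adjusted rank-based analysis (for example a rank analysis of covariance); otherwise use the Mann-Whitney test on change from T0. The rank-based version also avoids treating the steps of the MAS as equal. If the primary analysis is itself moved to T0 adjustment, use the same method for FMA-UE at T2. Settle the choice before between-group results are seen; if they are already known, report the analysis as chosen afterwards.

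The cost is a few lines of text and slightly more analysis work, with no new visits or data. The one downside is that a plain change score is noisier than the follow-up value for any measure whose correlation with T0 is below 0.5; the T0-adjusted version avoids this.

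### Randomisation is stratified on FMA-UE, but change is compared by an unadjusted Mann-Whitney test; adjusting for T0 would recover power if T0 has a monotone relation with change (optional, low severity)

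*Combined protocol and SAP*

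**What the plan says.** The Methods section of the combined protocol and SAP says "A randomization scheme was used to randomize participants" and then "To minimize possible confounding effects of upper limb motor ability, we stratified participants into groups based on upper limb motor function". The strata are "FMA UE score: 10-35 or a FMA UE score: 35-55", so a score of 35 belongs to both. The text does not say whether allocation was blocked within strata, or whether the stratifying score is the T0 score.

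Assessment times are set as follows: "Assessments were performed before training (T0), after training (T1), and 3 months after training (T2)". "The primary outcomes were changes in the FMA" upper-extremity score, total and distal, from T0 to T1. The remaining scales "at T1 and all measures at T2 were secondary outcomes".

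The Data Analysis section names one between-group method: the Mann–Whitney "U test was used to analyze differences between groups". The only other test is Wilcoxon's signed-rank, for baseline against post-training, which is not a comparison of arms. No covariate, stratum term or stratified rank test is named. The significance level is 0.05. No sample size, power, SD or expected effect is stated.

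**The concern.** The plan treats motor ability as important enough to control at allocation, then leaves it out of the analysis. The primary outcome is a change score, which subtracts T0. That does not remove an association between T0 and the amount of change, and any such association stays in the error term. Eligibility requires an "initial motor part of UE of FMA score ranging from 10 to 55", which leaves wide room for patients at different starting levels to change by different amounts. The document does not say whether they do.

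At stake is efficiency in a pilot. Noise that a baseline score already collected could explain would be left in the comparison. If allocation was balanced within strata, the unadjusted test would also reject less often than 5% under the null.

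**Working it through.** There is no stated power or sample size to reproduce, so the check is what adjustment would gain under stated assumptions.

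**Inputs from the document:** two arms; strata cut at FMA-UE 35; eligible range 10–55; outcome T0–T1 change; Mann–Whitney; α = 0.05.

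**Inputs assumed:** two-sided test; 1:1 allocation; N = 30 (15 per arm); true difference 4 points; residual SD 4 (the SD of change once T0 is accounted for); T0 uniform on 10–55; linear T0 effect with T0–change correlation r; blocks of 4 within strata unless stated.

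**Step 1: approximation by hand.** With residual SD 4, the unadjusted SD of change is 4/√(1 − r²). For a comparison of means, power ≈ Φ(δ/SD × √(n/2) − 1.96), with δ = 4 and n = 15. Adjusted: 4/4 × √7.5 = 2.739, and Φ(0.779) = 78.2% at every r. Unadjusted:

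| r | 1 − r² | SD of change | Power | Gain from adjustment |
|---|---|---|---|---|
| 0 | 1 | 4.00 | 78.2% | 0 |
| 0.3 | 0.91 | 4.19 | 74.3% | 3.9 |
| 0.45 | 0.7975 | 4.48 | 68.6% | 9.6 |
| 0.55 | 0.6975 | 4.79 | 62.8% | 15.4 |

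This ignores blocking, ties and the use of ranks, so it shows only the expected order of size.

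**Step 2: simulation of the rank tests** (normal errors, blocked). Mann–Whitney against rank-ANCOVA on ranked T0 plus stratum:

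| r | Mann–Whitney | Rank-ANCOVA (T0 + stratum) | Gain |
|---|---|---|---|
| 0 | 72.1% | 71.7% | −0.4 |
| 0.3 | 70.3% | 72.4% | 2.1 |
| 0.45 | 62.2% | 70.4% | 8.2 |
| 0.55 | 58.2% | 71.2% | 13.0 |

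Dropping the stratum term raises power by about 1–2 points and removes nearly all the cost at r = 0. With T0 alone the gain is about 0, 3–4, 8–9 and 15 points at the four values of r, in line with step 1.

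**Step 3: a different parameterisation.** Here the total SD of change is held at 4.5, the difference is 0.91 SD, there are 15 per arm, and adjustment is for T0 alone. Mann–Whitney against rank-ANCOVA: 62.2 vs 62.9 at r = 0; 63.9 vs 65.9 at 0.2; 62.1 vs 67.0 at 0.3; 63.6 vs 75.7 at 0.5. Mann–Whitney power hardly moves with r, so the shortfall is a gain not taken rather than a loss from some planned power.

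**Step 4: type I error.** In step 3 (blocked), Mann–Whitney rejects 5.1% of the time at r = 0 and 2.8% at r = 0.5; rank-ANCOVA rejects 5.5% and 5.0%. Under the step 2 assumptions Mann–Whitney rejects 2.7% at r = 0.55. With unblocked allocation it stays at 4.6–5.4% for every r examined, so the conservatism depends on balance within strata.

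**Step 5: a non-monotone relation.** T0 was made to predict change in an inverted-U shape, with r = 0.45 and the stratum term included. Mann–Whitney against rank-ANCOVA was 58.6 vs 61.0 (residual SD 4, blocked), 60.2 vs 60.6 (residual SD 4, unblocked), 71.4 vs 72.1 (total SD 4, blocked) and 71.6 vs 70.0 (total SD 4, unblocked). The gain runs from −1.6 to +2.4 points with a simulation error of about 1 point; separate runs gave −1.3 to +1.3. A ranked T0 term captures a rising or falling trend and little else.

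**The case against.** The strongest case for leaving the plan alone has four parts.

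First, nothing in it is wrong. A reader might infer that stratifying and then ignoring the strata biases the comparison or makes it invalid. It does not: randomisation protects the unadjusted test, and the only distortion found is towards too few rejections. This stands, and it limits the point to efficiency.

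Second, every quantity behind the gain is assumed. A reader might infer that the trial is underpowered, or that a planned power is being eroded. The document states no power target and calls the study a pilot, so neither inference is supported. Nothing in it indicates that r reaches 0.45, where the gain becomes noticeable; at r = 0.2 the gain in step 3 is 2 points. This stands too.

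Third, saying that T0 predicts the change is not a sufficient condition. Floor or ceiling effects could produce an inverted U, and step 5 shows that the gain then disappears. The point therefore holds only for a monotone relation.

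Fourth, the text is in the past tense, so the analysis may already have been done. The document does not settle whether outcome data have been seen, and the fix has to allow for both cases.

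What these objections do not remove is the asymmetry. Adjusting for T0 costs at most about 1 point of power if T0 is unrelated to change, and returns several points or more if a moderate monotone relation exists.

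**Conclusion.** The concern holds as an optional, low-severity improvement. The Mann–Whitney comparison is sound, but it leaves unused a baseline score that the plan itself considers relevant. The gain quoted in step 2 for T0-only adjustment (up to 15 points at r = 0.55) rests on N = 30, a difference of 4, residual SD 4 and a linear T0 effect, none of which the document supplies. The claim that Mann–Whitney falls below the nominal level rests further on allocation having been balanced within strata, which is not stated. No gain is quantified for the distal score or for any secondary measure.

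**What to change.** If outcome data have not been seen, add to the Data Analysis section wording such as: *For FMA-UE total, the T0–T1 change will be compared between arms by rank-ANCOVA. Change and T0 are each ranked over all patients, with average ranks for ties, and ranked change is modelled on arm and ranked T0. FMA-UE distal is analysed in the same way with its own T0 value. A Mann–Whitney test on change is a sensitivity analysis.* The same adjustment is optional for the secondary measures.

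Do not add a stratum term. It is a dichotomy of much the same score, and leaving it out also avoids having to decide where a score of 35 belongs. Do not treat ordinary ANCOVA as interchangeable: at N = 30 and r of 0.3 or less, simulated power was about 7–16 points below Mann–Whitney under skewed or heavy-tailed errors.

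If outcome data have been seen, keep Mann–Whitney as the primary test and report rank-ANCOVA as an added analysis, labelled as such.

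The cost is a few lines of text, a ranking step and one degree of freedom. No new data or patients are needed. Like Mann–Whitney, rank-ANCOVA yields a p-value and not a difference in FMA points.

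### Does it matter that the plan does not label a primary test or say whether the before/after signed-rank tests are per arm or pooled?

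*Combined protocol and SAP*

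**What the plan says.** The Aims section says that the study "aimed to investigate and compare the effects between Exoskeletal Robotic Hands therapy (RT") and the same training combined with mirror therapy (RMT). The Methods section gives the design: "After BoNT-A injection patients were randomly allocated to 2 groups: RT group, and RMT group". It adds that "both groups underwent 24 training sessions", so there is no arm without training and no arm with BoNT-A alone.

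On outcomes, Methods states "The primary outcomes were changes in the FMA", meaning its upper-limb part, specified as "total and distal scores) at T1 from T0". The remaining measures at T1, and every measure at T2, are secondary.

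Data Analysis is three sentences long. For the comparison of the arms it names Mann-Whitney: the "U test was used to analyze differences between groups". For change over time in the same patients it names Wilcoxon: the "signed-rank test was performed to assess differences in the parameters between baseline and post-training points". The third sentence begins "All tests were executed using the SPSS software version 25" and sets the significance level at 0.05. The section does not call either test primary, does not name the variable that enters the Mann-Whitney test, and does not say whether the signed-rank tests are per arm or pooled.

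**The concern.** The primary outcome is a change from T0 to T1, and both named tests can be applied to it. The signed-rank test asks whether the change differs from zero. The Mann-Whitney test asks whether it differs between RT and RMT. If both arms improve by a similar amount, the first can be significant when the second is not, and Data Analysis does not say which is the trial's main result.

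The design adds to the worry. All patients are injected and all are trained, so a before/after change may reflect BoNT-A, time, practice or regression to the mean as well as training. The plan also does not say whether T0 precedes or follows the injection. A report that led with significant before/after tests could therefore credit RT or RMT with an effect that this design cannot isolate, or could read significance in one arm only as a difference between the arms.

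**Working it through.** The plan gives no sample size, power, effect size or standard deviation, so it has no figure to reproduce. The check has three parts.

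**1. Can the primary comparison be identified from the text?**

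- Title and Aims: compare RT with RMT.
- Methods: patients are randomised to those two arms only.
- Methods: the primary outcome is change in FMA-UE (total and distal) from T0 to T1.
- Data Analysis: Mann-Whitney is the test for between-group differences.

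Together these give one reading: Mann-Whitney on the T0-to-T1 change, RT against RMT, for FMA-UE total and distal. The variable is not open either, because Methods defines the primary outcome as the change.

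**2. How many tests are affected?**

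The named measures are FMA-UE total, FMA-UE distal, MAS, MRC, ARAT, BBT and MAL, which makes 7. Assume one score per measure and both tests at both T1 and T2; the plan states neither.

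| | Mann-Whitney | Signed-rank, pooled | Signed-rank, per arm |
|---|---|---|---|
| Primary outcomes, T1 | 2 | 2 | 2 × 2 = 4 |
| All measures, T1 and T2 | 7 × 2 = 14 | 7 × 2 = 14 | 7 × 2 × 2 = 28 |

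Before/after tests are thus 2/4 = 50% or 4/6 = 67% of the primary-outcome p-values, and 14/28 = 50% or 28/42 = 67% overall. These shares follow from naming two kinds of test. They measure no bias and no error rate.

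**3. What would go wrong if the before/after tests were misread?**

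Suppose both arms truly change equally and each per-arm signed-rank test has power *p*. The chance that exactly one arm is significant is 2*p*(1 − *p*):

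- *p* = 0.2: 2 × 0.2 × 0.8 = 0.32
- *p* = 0.5: 2 × 0.5 × 0.5 = 0.50
- *p* = 0.8: 2 × 0.8 × 0.2 = 0.32
- *p* = 0.9: 2 × 0.9 × 0.1 = 0.18

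If neither arm changes, two independent per-arm tests at 0.05 give at least one false positive with probability 1 − 0.95² = 0.0975.

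A simulation shows the contrast between the tests. It used normal changes with standard deviation 1, the same mean change in both arms and 2,000 runs per setting. The arm sizes and effects are assumptions, not plan values. Entries are the proportion of runs significant at 0.05.

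| n per arm | Standardised change in both arms | Signed-rank, per arm | Signed-rank, pooled | Mann-Whitney on change |
|---|---|---|---|---|
| 10 | 0.5 | 0.298 | 0.548 | 0.041 |
| 10 | 0.8 | 0.599 | 0.911 | 0.038 |
| 15 | 0.5 | 0.414 | 0.731 | 0.044 |
| 15 | 0.8 | 0.798 | 0.985 | 0.041 |
| 20 | 0.5 | 0.565 | 0.853 | 0.054 |
| 20 | 0.8 | 0.915 | 0.996 | 0.053 |

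The signed-rank tests detect the shared change, as they should. Mann-Whitney stays near its nominal 5% whatever the shared change. The per-arm or pooled choice moves the signed-rank column and leaves the Mann-Whitney column untouched. BoNT-A, time and practice act in both arms, so randomisation covers them in the comparison that the trial sets out to make.

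**The case for a change.** The best case for a change is that an analysis section should state its hierarchy and not leave it to be inferred. The aim is to investigate as well as to compare, which leaves some room to treat before/after tests as answers in their own right. The simulation shows that the two kinds of test will often disagree when both arms improve. Two or three sentences would settle the matter and would cost nothing in conduct, tests or software.

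Part of this stands. The label is missing, the per-arm or pooled choice is missing, and writing both down would do no harm. But each test already has its own stated question, and the disagreement arises only if a reader takes the answer to one as the answer to the other. The plan does not do so: it nowhere attributes a before/after change to RT or RMT. For the primary outcome the caution is also weaker than it appears, because the Background describes BoNT-A as not improving arm and hand capacity. It is strongest for MAS, which is secondary. Data Analysis is written in the past tense; if the results were already known, a label added now would not be pre-specification.

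**Conclusion.** The concern does not call for a change. The omission is real, but the rest of the document fills it: the RT-versus-RMT conclusion rests on the Mann-Whitney comparison of T0-to-T1 change in FMA-UE, total and distal. Followed as written, the plan gives a sound answer to that question. Whether the signed-rank tests are per arm or pooled affects only a supporting description, and a competent analyst will state in the report which was done. The lack of an untrained or BoNT-A-only arm is no defect for a trial that compares two trainings; it limits how a before/after change may be read, and the plan makes no claim beyond that limit.

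The effect on the between-group result is nil. The shares of 50% and 67% are counts of tests, and the simulated rejection rates rest on assumed arm sizes, effects and normality. The conclusion depends on one reading, namely that the title, aim, randomised arms and outcome definition together fix the primary comparison. It would change if the plan claimed an effect of either training from before/after tests alone.
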